# 10.2 Dose Escalation Procedures and Stopping Criteria

### **10.2.1 Dose Escalation Procedures (Part A and Part B)**

Following completion of each cohort in Part A, a summary of all available safety (AE, 12-lead ECG, vital signs and safety laboratory data) and 24 hour post last dose PK data (minimally Cmax and AUC0-24 data) will be produced on behalf of the PI. Planned doses may be modified following a review of emerging data. Progression to the next dose level and dose selection will be based on the available safety and PK data from all evaluable 9 subjects from the preceding dose level (a subject will be deemed as evaluable for dose escalation purposes if they have received the planned study dose and had sufficient plasma samples collected to estimate Cmax and AUC0-24 irrespective of whether they have received active or placebo treatment). Dose escalation will be dependent upon the accrual of acceptable safety and PK data. If it is not appropriate to escalate the dose according to the proposed dose escalation schedule, then the same dose, an intermediate dose or a lower dose may be given following discussion between the Sponsor and the PI (or deputy).

There will be a Telephone Conference at a pre-appointed time to involve the Simbec-Orion Project Manager and the PI (or deputy) and the Sponsor's representative(s), including the Sponsor's Responsible Physician. After discussion of all the data, the decision will be made whether to dose escalate and a written document (dose escalation approval form) signed by the PI (or deputy) and Sponsor will be produced ratifying that decision. Full minutes, to be agreed by all parties, will be produced for each discussion regarding dose escalation and filed in the investigator site file (ISF). A copy of the signed dose escalation approval form will be provided to the Simbec-Orion Pharmacist and this will allow the IMP to be assembled for the next dose level.

Part B dosing regimen will be decided after reviewing all available Part A safety and PK data following the same rules and procedures as for Part A.

Dose escalation stopping criteria are detailed in Section 10.2.2.

DNDi RD 777/34920 DNDi- 0690- 02

Final V3.0/ Date 07 December 2020

Confidential

Page 49 of 109

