### Part A: Multiple Ascending Dose Cohorts (Cohorts 1-4)

Part A will consist of up to 4 cohorts of 9 subjects. Subjects will be randomly assigned to receive an oral dose of active IMP (6 subjects) or matching placebo (3 subjects) for 10 days in a sequential escalating manner with a minimum of 7 days interval between two cohorts.

In Part A, each cohort will follow a sentinel dose-escalation schedule; two (2) subjects will be dosed on the first dosing day of each cohort (1 subject on active IMP and 1 subject on matching placebo). The remainder of the cohort (5 subjects on active IMP and 2 subjects on matching placebo) will be dosed a minimum of 48 hours later pending confirmation of an acceptable safety profile in the dose-leader cohort by the Principal Investigator (PI), or medically-qualified designees who are familiar with the study protocol and Investigator's Brochure (IB).

The planned starting dose for Cohort 1 is 400 mg of DNDI-0690 once a day for 10 days. Doses to be administered in Cohorts 2 to 4 will be determined based on emerging PK and safety data. The number of daily doses may be increased to 2 by implementation of a twice a day (BID) dosing regimen if the number of capsules in a single intake is raising concerns of acceptability. This decision will be made by the Safety Review Committee (SRC) prior to each cohort and will apply to all subjects within a cohort.

Dose escalation between cohorts in Part A (and between Part A and Part B) will be temporarily stopped pending evaluation of all available data if any of the following criteria are fulfilled:

• A serious adverse reaction (*i.e.* a serious adverse event (SAE) considered at least possibly related to the IMP administration) occurs in one subject.

Or

• Severe non-serious adverse reactions (*i.e.* severe non-serious AE considered as, at least possibly related to the IMP administration) occur in two subjects in the same cohort, independent of within or not within the same system organ class.

Or

- If two or more subjects in the preceding dose group experience any of the following:
  - Alanine aminotransferase (ALT) or aspartate aminotransferase (AST) >3x upper limit of normal (ULN), considered clinically significant and IMP related.
  - Serum Cystatin C (Cys C) increase > 25%, confirmed after repeat assessment 24-48h apart, and considered IMP related.
  - o Ratio of microalbuminuria/creatininuria >300 mg/g and considered IMP related.

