#### Day 10:

On Day 10, only a morning dose will be administered.

- Start Holter monitoring (for extraction of ECGs) at approximately 60 minutes prior to dosing (Holter will be on for at least 25 hours and can only be removed after 24 h post-last dose PK blood samples are collected)
- Eligibility check: Pre-dose
- O Dosing (morning only on Day 10, even if BID regimen implemented)
- Laboratory safety tests (biochemistry, haematology, coagulation, urinalysis, urine microscopy): Pre-dose
- o Troponin I: Pre-dose
- o 12-lead ECG: Pre-dose and 4 h post-dose
- Vital signs (supine systolic and diastolic blood pressure, pulse rate and tympanic temperature):
   Pre-dose
- o AE
- o SAE
- Prior and concomitant medication
- PK plasma sample for DNDI-0690 and metabolite: Pre-dose and 0.5, 1, 2, 3, 3.5, 4, 6, 9, 12 h post-dose
- O DBS samples for DNDI-0690: Pre-dose and 0.5, 1, 2, 3, 3.5, 4, 6, 9, 12 h post-dose
- o PK urine samples for DNDI-0690:[0-24] h post-dose
- Urine samples for exploratory biomarkers: Pre-dose
- Full blood sampling for transcriptional profiling (mRNA) assessment (**Only performed on Cohort 2 and Cohort 3**)

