# ABBREVIATIONS USED IN THE PROTOCOL TEXT

**DND**i

RD 777/34920

DNDi- 0690- 02

Abbreviation	Definition
ABPI	The Association of the British Pharmaceutical Industry
ADR	adverse drug reaction
AE	adverse event
ALB	Albumin
ALP	alkaline phosphatase
ALT	alanine aminotransferase
AmpB	amphotericin B
ANOVA	analysis of variance
API	The active pharmaceutical ingredient
aPTT	activated partial thromboplastin time
AST	aspartate aminotransferase
AUC	area under the concentration versus time curve
$AUC_{0-24}$	AUC from time zero to time 24 h post-dose
$\mathrm{AUC}_{0 ext{-inf}}$	AUC extrapolated to infinity from dosing time, based on
	the last measurable concentration
$AUC_{0\text{-last}}$	AUC from the time of dosing to the time of the last
	measurable concentration
$\mathrm{AUC}_{0\text{-} au}$	AUC from time of dosing to the end of the dosing interval
BIA	The BioIndustry Association
BID	twice a day
BMI	body mass index
BUN	blood urea nitrogen
CCRA	The Clinical Contract Research Association
CL	cutaneous leishmaniasis
CNS	central nervous system
COVID-19	coronavirus disease 2019
$C_{max}$	maximum concentration
$C_{max, norm}$	maximum concentration divided by dose per kilogram
	body weight
$C_{max, SS}$	maximum concentration at steady state
$C_{\min, SS}$	minimum concentration at steady state
CRF	case report form
eCRF	electronic case report form
CV%	coefficient of variation
CYP	Cytochrome P450
Cys C	Cystatin C
DDI	drug-drug interaction
DMP	data management plan
DOA	drugs of abuse
EC	Ethics Committee
ECG	electrocardiogram
EDTA	ethylenediaminetetraacetic acid
EMA	European Medicines Agency
Fe (%)	% mean cumulative urine

Confidential

RD 777/34920 DNDi- 0690- 02

DNDi

Final V3.0/ Date 07 December 2020

Page 31 of 109

FDA	US Food and Drug Administration
FIH	First-in-Human
FSH	follicle-stimulating hormone
GCP	Good Clinical Practice
GDPR	General Data Protection Regulation
GFR	glomerular filtration rate
GFRcc	glomerular filtration rate based on serum cystatin C levels
GFRe	glomerular filtration rate based on serum creatinine levels
mGFR	measured glomerular filtration rate
GGT	gamma glutamyl transferase
GI	gastrointestinal
GLP	Good Laboratory Practice
GMP	Good Manufacturing Practice
GP	general practitioner
HBsAg	hepatitis B surface antigen
HCV Ab	hepatitis C virus antibody
HDPE	high density polyethylene
HED	human equivalent dose
hERG	the human Ether-à-go-go-Related Gene
HIV	human immunodeficiency virus
HPMC	hydroxypropyl methylcellulose
HR	heart rate

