A Pathology Working Group (PWG) was constituted to review the data on testes. For the 7–day study, the PWG concluded that the testicular effect of vacuolation was a background change and that the effects seen were all considered as fixation artefact and thus the testicular histology was all concluded to be within the normal. In the case of the 28-day study, the PWG confirmed following review the presence of changes in the testes of animals at the two highest doses of 100 and 400 mg/kg/day (the same animals as in the initial report) where the finding was described by the PWG as segmental tubular dilation with associated thinning/atrophy of the seminiferous epithelium. This distribution could suggest a potential relationship to treatment. However, based upon the segmental nature of the finding, the frequent unilateral distribution and the fact that this finding has been described in a number of publications as a background change in young cynomolgus monkeys, it was concluded that the findings in the testes were a background lesion and unrelated to treatment. In conclusion, treatment with DNDI-0690 for 7 or 28 days is not considered to induce any testicular changes or toxicity.

Confidential

Final V3.0/ Date 07 December 2020

Page 40 of 109

Table 3 Summary of Toxicokinetic and Pharmacokinetic Parameters for DNDI-0690\*

Species / Day	Gender	Type of study	Dose PO (mg/kg/day)	C max (µg/mL)	AUC 0-24 (μg.h/mL)
Rat /	M	Toxicology TK	1000 (500 bid) NOAEL 28 days	$11.3 \pm 0.693$	180 ± 22.5
Day 28	F	Toxicology TK	1000 (500 bid) NOAEL 28 days	16.9 ± 1.47	307 ± 36.8
Monkey /	M Toxicology TK		20 (10 bid) NOAEL 28 days	$8.03 \pm 0.367$	101 ± 7.85
Day 28	F	Toxicology TK	20 (10 bid) NOAEL 28 days	$9.03 \pm 6.78$	111 ± 61.2

\* methodology, additional doses and time-points available in the IB

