### 8.7 Risk/Benefit Assessment

No benefit will be observed in healthy volunteers.

The risk/benefit ratio of the proposed study is considered acceptable. Several measures to minimize the risks to healthy subjects have been taken with respect to the following study design elements:

- For each cohort in Part A and Part B, 2 subjects (1 subject on active drug and a subject on matching placebo) will be dosed and monitored for 48 hours prior to dosing the rest of the cohort.
- Dose escalation (during Part A and between Part A and Part B) will be done in a stepwise, controlled manner, with dose escalation only being permitted after full evaluation of the available safety data from the previous cohort by the SRC.
- Clinical laboratory monitoring: At time of study entry, study participants are required to have safety laboratory values within acceptable ranges. Serial measurements of safety laboratory parameters (Biochemistry and haematology which include platelet count, renal/liver function tests, renal integrity monitoring) and coagulation parameters are planned with interim reviews as defined in the SRC charter.
- Close cardiac safety monitoring by regular ECG assessments.
- Study eligibility: The healthy subject/patient inclusion and exclusion criteria have been incorporated to minimize any risk of an exaggerated pharmacological effect of DNDI-0690.
- The evaluation of GFR by a reference method in Part C will be performed at the end of the trial. The dose level used in Part C will be tested in Part A and will have no impact on the safety of the volunteers.
- The starting dose in Part A of this study is 400 mg once daily for 10 days which is considered to be safe and is well below the highest dose level of 3600 mg DNDI-0690 administered in the SAD study. It is expected that the maximum values of  $C_{max}$  and  $AUC_{0-24}$  in individual subjects in Part A Cohort 1 will be well below the PK stopping criteria of  $C_{max} \ge 8000$  ng/mL or  $AUC_{0-24} \ge 100,000$  ng,h/mL.

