#### 10.2.2.3 Dose Escalation Stopping Criteria

Dose escalation between cohorts in Part A (and between Part A and Part B) will be temporarily stopped pending evaluation of all available data if any of the following criteria are fulfilled:

• A serious adverse reaction (*i.e.* a SAE considered at least possibly related to the IMP administration) occurs in one subject.

Or

• Severe non-serious adverse reactions (*i.e.*, severe non-serious AE considered as, at least possibly related to the IMP administration) occur in two subjects in the same cohort, independent of within or not within the same system organ class.

Or

• If two or more subjects in the preceding dose group experience any of the following:

DNDi RD 777/34920 DNDi- 0690- 02

Final V3.0/ Date 07 December 2020

Confidential

Page 50 of 109

- o ALT or AST >3xULN, considered clinically significant and IMP related.
- Serum Cys C increase > 25%, confirmed after repeat assessment 24-48h apart, and considered IMP related.
- o Ratio of microalbuminuria/creatininuria >300 mg/g and considered IMP related.
- o an increase in QTcF value of >60 msec from baseline (average of baseline triplicate values) or an absolute QTcF >500 msec, both confirmed by repeat measurement after 20 minutes in resting position, and considered IMP related.

Or

- If one or more subjects in the preceding dose group experience:
  - o an increase in troponin I concentration which is considered clinically significant by the Investigator (with reference to the change from baseline value) and considered IMP related.

Or

• If the dose in a single subject is anticipated to exceed an AUC0-tau of  $\geq 100 \, \mu g^*h/mL$ . These limits are based on the exposure observed at the 20 mg/kg in cynomolgus monkeys (NOAEL: AUC0-24 of 101  $\mu g^*h/mL$  in male and 111  $\mu g^*h/mL$  in females).

Or

• If the dose in a single subject is anticipated to exceed a  $C_{max}$  of  $\geq 8.0 \ \mu g/mL$ . These limits are based on the exposure observed at the 20 mg/kg in cynomolgus monkeys (NOAEL:  $C_{max}$  of  $8.03 \ \mu g/mL$  in males and  $9.03 \ \mu g/mL$  in females).

Dose escalation between cohorts in Part A will be limited to a maximal 3-fold increase, and 2-fold increase between Part A and Part B, depending on safety and tolerability data and predicted exposure (both AUC and  $C_{max}$ ).

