### Twice daily dosing (BID) regimen if needed:

- If a BID regimen is implemented, subjects will fast overnight for at least 10 hours (h) before each morning dose.
- The second, evening dose will be administered 10 hours following the morning dose. The second, evening dose shall be taken a minimum of 5 hours post mid-day meal, and one hour before the dinner.
- On Day 10, only a morning dose will be administered.
- Lunch will be served: approximately 4 h post-morning dose.
- Receive second, evening dose of the day: 10 h post-morningdose
- Dinner will be served: approximately 12 h post-morningdose.

On all non-dosing study days, whilst resident in the clinical unit, meals will be served at standard times. Subjects will choose meals from a standard menu while resident at the clinical unit.

Subjects are required to fast for at least 8 h or 10 h prior to laboratory sample collection for the following tests:

• For blood glucose tests (analysed in serum), require at least 8 h fasting period for fasted glucose test.

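### If a Part A cohort is dosed twice daily, the AUC cap refers to one dosing interval although it comes from a 24 h exposure, and the required Day 10 AUC0-24 leaves out the evening dose

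*Protocol*

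**What the plan says.** **Regimen.** The Synopsis (Part A) allows a change of regimen: "The number of daily doses may be increased to 2 by implementation of a twice a day (BID) dosing regimen", if the capsule count raises acceptability concerns. Section 10.5.3.1 fixes the spacing: "The second, evening dose will be administered 10 hours following the morning dose". The two intervals are therefore 10 h and 14 h. On the last day the Synopsis specifies "Dosing (morning only on Day 10, even if BID regimen implemented".

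**Escalation input.** Section 10.2.1 requires "a summary of all available safety (AE, 12-lead ECG, vital signs and safety laboratory data) and 24 hour post last dose PK data", with Cmax and AUC0-24 as the least that must be supplied. It makes no adjustment for BID. Section 10.9.2.5.4 adds AUC0-10 for BID on Days 1 and 10. On Days 2 to 9 the only plasma samples are taken before the morning dose.

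**Cap.** The Synopsis and Section 10.2.2.3 stop escalation if a subject is anticipated to exceed an AUC0-tau of 100 µg·h/mL. Section 5 defines AUC0-tau as "AUC from time of dosing to the end of the dosing interval". On the origin of the limits, Section 10.2.2.3 says "These limits are based on the exposure observed at the 20 mg/kg in cynomolgus monkeys", and cites AUC0-24 values of 101 (males) and 111 (females) µg·h/mL. Table 3 gives that regimen as "20 (10 bid) NOAEL 28 days". Section 8.7 expects Cohort 1 maxima that "will be well below the PK stopping criteria of" Cmax 8000 ng/mL or AUC0-24 100,000 ng·h/mL. The same limit is thus named there as a 24 h quantity.

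**The concern.** Under once-daily dosing tau is 24 h, so all these statements agree. Under BID they separate in two ways.

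- The cap is compared with the AUC of one human dosing interval, while its source is a full day containing two animal doses.
- The one AUC that must reach the people deciding on escalation describes a day with one dose, although subjects received two doses on each of the nine days before.

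Both errors make exposure look lower than it is. The cap ties healthy subjects to the monkey no-effect exposure of a drug whose main toxicity target is the kidney, so the quantity it is applied to should match its source.

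**Working it through.** **Reproducing the plan.** Table 4 accumulation ratio = predicted AUC0-tau (once daily) / single-dose AUC0-24:
- 400 mg: 13,100/11,800 = 1.11
- 1200 mg: 23,600/19,700 = 1.20
- 3600 mg: 44,900/32,800 = 1.37

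All three match the table.

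**Inputs (Table 4, fasted males, single dose, ng·h/mL).**

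| Dose | AUC0-12 | AUC0-24 | AUC0-inf |
|---|---|---|---|
| 400 mg | 8,500 | 11,800 | 13,900 |
| 1200 mg | 13,400 | 19,700 | 25,100 |

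The method is linear superposition, as in Section 10.3.1, with doses at 0 and 10 h and a mono-exponential decline from about 10 h.

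**Step 1: terminal slope.** λ = ln(1 + AUC12-24/AUC24-inf)/12
- 1200 mg: ln(1 + 6,300/5,400)/12 = 0.0644 per h
- 400 mg: ln(1 + 3,300/2,100)/12 = 0.0787 per h

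**Step 2: what the omitted evening dose would have contributed in its 14 h.** AUC0-14 = AUC0-12 + AUC12-inf × (1 − e^(−2λ))
- 1200 mg: 13,400 + 11,700 × 0.121 = 14,815
- 400 mg: 8,500 + 5,400 × 0.146 = 9,286

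**Step 3: daily AUC against Day 10 AUC0-24.** Steady-state daily AUC = 2 × AUC0-inf. Day 10 AUC0-24 = daily AUC − AUC0-14.

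| Regimen | Daily AUC | Day 10 AUC0-24 | Ratio | Shortfall |
|---|---|---|---|---|
| 1200 mg BID | 50,200 | 35,385 | 0.705 | 29.5% |
| 400 mg BID | 27,800 | 18,514 | 0.666 | 33.4% |

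Using Table 4's predicted AUC0-tau for 1200 mg instead gives a daily AUC of 2 × 23,600 = 47,200 and a Day 10 value of 32,385, a ratio of 0.69. Without the tail assumption, AUC0-14 must still lie between AUC0-12 and AUC0-24. The 1200 mg shortfall then lies between 13,400/50,200 = 26.7% and 19,700/50,200 = 39.2%.

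**Step 4: what an AUC0-tau of 100 means per day.** Let R(t) = AUC12-inf × e^(−λ(t−12)) be the AUC remaining after time t from one dose. At steady state, the AUC of the 10 h interval = AUC0-inf − R(10) + [R(14) − R(34)]/(1 − e^(−24λ)).
- 1200 mg: 11,791 + (10,285 − 2,835)/0.787 = 21,258, or 42.3% of the day. The 14 h interval has 28,942, or 57.7%.
- 400 mg: 11,889, or 42.8%. The 14 h interval has 15,911, or 57.2%.

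Daily AUC when AUC0-tau = 100 µg·h/mL:
- 10 h interval: 100/0.423 = 236 and 100/0.428 = 234, so about 235
- 14 h interval: 100/0.577 = 173 and 100/0.572 = 175, so about 174

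The monkey source is 101 to 111.

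**Step 5: could individuals be near the cap?** Take a log-normal daily AUC at 1200 mg BID with geometric mean 47,200 to 50,200, and σ = √ln(1 + CV²).
- CV 64% (1200 mg row): σ = 0.586, and 10 to 12% of subjects exceed 100,000.
- CV 23.5% (3600 mg row): σ = 0.232, and 0.2% or fewer do.

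**Cmax.** One- and two-compartment oral profiles fitted to the 1200 mg row put the evening peak at about 2,930 to 3,130 ng/mL, against 2,680 to 2,890 in the morning. Both are far below 8,000, so the issue is AUC.

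**The case against.** Several points on the other side have force.

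- **The trigger is narrow.** BID is used only if the number of capsules becomes a problem. The top scheduled Part A dose of 2400 mg/day is 12 capsules of 200 mg, and 18 were given in the single-dose study.
- **The required PK is a minimum.** Section 10.2.1 calls for discussion of all the data. The Day 1 profile, daily troughs, AUC0-10 and the decline to Day 12 are available. That is true, but nothing requires a steady-state daily AUC under BID.
- **The cap concerns anticipated exposure.** A reader might infer that a subject with an observed Day 10 value of 66 to 71 µg·h/mL has already met the cap unnoticed. The text does not support this, because the observed value is not the cap's stated input. Exposure can be predicted properly, but the predicted quantity is still written as AUC0-tau.
- **The shortfall can be offset.** In going from 400 to 1200 mg BID, dose-proportional scaling gives 3 × 18.5 = 55.5 µg·h/mL. That is more than the 50.2 expected, because exposure rises less than proportionally.
- **Section 8.7 speaks of Cohort 1.** That cohort is once daily, where the two metrics coincide. The sentence shows how the criterion was understood, but does not settle the BID case.

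Three further inferences are tempting and should not be drawn:

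- **Hidden accumulation.** Accumulation is planned on Cmax and AUC0-tau, and AUC0-10 gives matched intervals under BID.
- **A misjudged step to Part B.** A low BID figure would make the step look larger, which invites caution. The 3600 mg once-daily dose also has its own prediction in Table 4.
- **Loosened fold limits.** Table 1 expresses these as multiples of dose, which a low AUC does not change.

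**Conclusion.** The point stands, but only for a Part A cohort dosed BID. The mismatch in the cap and the missing evening dose follow from the text and need no modelling. Their size does: about 235 or 174 µg·h/mL per day allowed by a literal reading of the cap, and a required AUC0-24 about 30% too low. These figures rest on linear superposition of fasted male geometric means and on the evening dose being absorbed like the morning dose.

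The documents do not show that a cohort would exceed the monkey exposure. Predicted mean daily AUC at 1200 mg BID is about half the cap, and the share of individuals above it runs from 0.2% or less to about 12%, depending on which Table 4 CV applies. This is a wrongly stated safety threshold and an incomplete required input, both cheap to correct before any BID cohort opens.

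**What to change.** - **Synopsis and Section 10.2.2.3:** state the AUC cap as steady-state AUC0-24 for both once-daily and BID dosing, as Section 8.7 already does.
- **Section 10.2.1:** for any BID cohort, label the Day 10 AUC0-24 as morning-dose-only. Add, per subject, the superposed steady-state 24 h AUC and evening Cmax by the method of Section 10.3.1, and judge anticipated exposure against both caps from these. The Day 1 profile before the evening dose and the Day 10 to 12 decline supply the inputs.

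The cost is a change of wording and one calculation per BID cohort, with no extra samples, visits or subjects.

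The downside is that the added values are predictions and should be labelled so. They assume linearity over time and equal evening absorption. The evening dose is taken at least 5 h after lunch and 1 h before dinner, without an overnight fast. Fed exposure in the single-dose study was 67 to 75% higher (Section 8.6.1), so the predictions may understate evening exposure.
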